8.4.4 Additional potential data sources

Beside the data sources evaluated originally in the UK, Sweden, and Finland, none of the holders of other databases have been contacted for participation in the study so far, and further feasibility assessments are required to insure the validity of urinary cancer case identification. It is important for the choice of the appropriate data source to have the appropriate information on cancer and important risk factors included.

Potential additional data sources for this study have been assessed ([Annex 1](#)). In addition to those described above, Danish nationwide registers, PHARMO Database Network (Netherlands), Spanish regional registers, and Maccabi Healthcare Services database (Israel) are feasible for inclusion in the study.

8.5 STUDY SIZE

The study size will be driven by the uptake of empagliflozin and the primary comparator (DPP-4 inhibitors) in the UK, Sweden, and Finland. Originally, it was expected that by the end of 2019, approximately 18,000 empagliflozin-treated patients will accumulate in the CPRD and Swedish databases. However, based on the conservative estimates from the fifth interim analysis ([Annex 1](#)), the expected sample size is higher than anticipated. Taking into account the addition of Finland, the addition of CPRD Aurum, and the extension of the study period (end of 2020 for Sweden and Finland, end of 2021 for CPRD), a total of approximately 67,490 empagliflozin users are expected to be eligible for inclusion in the study ([Table 6](#)). However, the number of patients available for analysis may be lower. Given the observed patient numbers, it is expected that the maximum achievable matching ratios will be 1:3 for UK CPRD (GOLD and Aurum), 1:1 for Sweden, and 1:2 for Finland.

Table 6

Observed and expected number of patients eligible for inclusion in the study population, by study drug group (including fixed-dose combinations with metformin), by study country and overall, using an arithmetic growth assumption.

Year	Study drug group	Finland	Sweden	CPRD GOLD	CPRD Aurum ⁴	Pooled
2014 ¹	Empagliflozin	0	0	5		5
	DPP 4-inhibitors	5,824	3,214	2,555		11,593
	Other SGLT-2 inhibitors	127	662	683		1,472
2015 ¹	Empagliflozin	91	629	157		877
	DPP 4-inhibitors	14,130	10,305	6,851		31,286
	Other SGLT-2 inhibitors	320	1,537	2,065		3,922
2016 ¹	Empagliflozin	2,201	2,181	897		5,279
	DPP 4-inhibitors	11,391	12,126	5,648		29,165
	Other SGLT-2 inhibitors	1,463	1,183	1,740		4,386
2017 ¹	Empagliflozin	3,725	4,811	1,391		9,927
	DPP 4-inhibitors	7,402	13,677	4,577		25,656
	Other SGLT-2 inhibitors	1,475	1,191	1,493		4,159
2018 ¹	Empagliflozin	4,293	8,738	1,536		14,567
	DPP 4-inhibitors	6,959	12,798	4,158		23,915
	Other SGLT-2 inhibitors	1,610	1,030	1,470		4,110
2019 ¹	Empagliflozin	5,182	10,169	1,846		17,197
	DPP 4-inhibitors	6,158	11,673	3,622		21,453
	Other SGLT-2 inhibitors	1,853	1,061	1,665		4,579
2020 ²	Empagliflozin	2,777	5,806	1,541		10,124
	DPP 4-inhibitors	2,215	4,688	2,210		9,113
	Other SGLT-2 inhibitors	1,201	653	1,369		3,223
2021 ³	Empagliflozin			969		
	DPP 4-inhibitors			1,051		
	Other SGLT-2 inhibitors			726		
Total	Empagliflozin	18,269	32,334	8,342	8,545	67,490
	DPP 4-inhibitors	54,079	68,481	30,672	59,283	212,515

Year	Study drug group	Finland	Sweden	CPRD GOLD	CPRD Aurum ⁴	Pooled
	Other SGLT-2 inhibitors	8,049	7,317	11,211	25,277	51,854

1 Observed number of patients.

2 Observed number of patients until 30th June for Sweden and Finland and until 31st December for UK CPRD GOLD, taking into account the extension of the study period to the end of 2021 for UK CPRD.

3 Expected number of patients (arithmetic growth assumption given observed numbers in previous years) between 1st January and 30th June, taking into account the 6 months minimum follow-up.

4 Only aggregate level data up (2014-2020) of was available for CPRD Aurum. Patient numbers were extrapolated based on assumptions derived from CPRD GOLD data, taking into account the extension of the study period to the end of 2021
DPP-4=dipeptidyl peptidase-4 inhibitors; SGLT-2=sodium glucose co-transporter-2 inhibitors; UK=the United Kingdom

The power to detect relative risks of 1.5 and 2 was determined for each of the study outcomes for each individual country ([Table 7](#)) and for the final random-effects meta-analysis ([Table 8](#)). For the single-country analyses, power computations were based on HRs derived from Cox models. For the meta-analysis, simulations were used to estimate country-level HRs which were then entered into random-effects meta-analysis models as described in [Section 8.7.1.4](#). All power computations were based on the expected number of individuals exposed to empagliflozin eligible for inclusion in the study and the observed country-level IRs of urinary tract cancers, bladder cancer and renal cancer in the study population as reported in the 5th Interim Report. The expected averages of follow-up time were 2.4 years for UK CPRD, 2.2 for Sweden, and 2.4 for Finland, as reported in the 5th Interim Report. Matching ratios of empagliflozin initiators to initiators of DPP-4 inhibitors were fixed at 1:3 for UK CPRD, 1:1 for Sweden, and 1:2 for Finland. These are the highest achievable matching ratios given expected patient numbers. For computing the meta-analysis power, these assumptions were used to simulate for each country separately individual level time-to-event data from each drug cohort following an exponential distribution given the expected number of empagliflozin initiators, the expected matching ratio, the observed incidence rates as the baseline rate in the DPP-4 cohort. The hazard ratio for each simulation run was determined by drawing from a normal distribution with a mean of the natural logarithm of the target hazard ratio (1.5 or 2.0) and a standard deviation of 0.1. These individual time-to-event data were then entered into a Cox proportional hazard model for each country to compute a simulated hazard ratio. For each simulation, the country-level hazard ratios were entered into a random-effects meta-analysis level, and the resulting p-value of the pooled estimate was retained. Simulations were run 500 times and power was computed as the proportion of simulations for which the p-value of the pooled estimate was inferior to 0.5.

The power calculations show that anticipated study sample size would ensure sufficient power at the meta-analysis level to detect the targeted effect size of < 1.6 for urinary tract cancers and bladder cancer and the targeted effect size of < 2.0 for renal cancer, with at least 80% power and a type 1 error probability of 5% under the expected matching ratios. Power at the meta-analysis level to detect an effect size of 1.5 is expected to be of 93.6% for urinary tract cancer and 84.0% for bladder cancer. Power at the meta-analysis level to detect an effect size of 2.0 is expected to be of 97.0% for renal cancer.

Table 7

Power for different effect sizes for single-country analyses based on Cox models with a type 1 error probability of 5%, given country-level observed incidence rates, expected numbers of empagliflozin initiators, expected follow-ups, and expected matching ratios.

Effect size (Hazard ratio)	Urinary tract cancer	Bladder cancer	Renal cancer
UK CPRD¹			
1.5	63.7%	43.1%	20.3%
2.0	99.1%	91.7%	55.9%
Sweden²			
1.5	85.1%	66.6%	42.9%
2.0	>99.9%	99.0%	89.4%
Finland³			
1.5	80.6%	54.3%	46.7%
2.0	99.9%	96.8%	93.4%

1 Includes both CPRD GOLD and Aurum; Observed IRs of 111.5, 66.7, and 26.5 per 100,000 person-years for UTC, bladder cancer, and renal cancer respectively, expected follow-up of 2.4, matching ratio of 1:3, and expected number of empagliflozin initiators of 16,360.

2 Observed IRs of 164.5, 104.1, and 58.0 per 100,000 person-years for UTC, bladder cancer, and renal cancer respectively, expected follow-up of 2.2, matching ratio of 1:1, and expected number of empagliflozin initiators of 32,334.

3 Observed IRs of 161.5, 86.8, and 71.6 per 100,000 person-years for UTC, bladder cancer, and renal cancer respectively, expected follow-up of 2.4, matching ratio of 1:2, and expected number of empagliflozin initiators of 18,269.

UK CPRD=The United Kingdom Clinical Practice Research Datalink

Table 8

Power of meta-analyses for a type 1 error probability of 5% for different effect sizes, given country-level observed incidence rates, expected number of empagliflozin initiators, expected average follow-ups, and expected matching ratios.

Effect size (Relative risk / hazard ratio)	Urinary tract cancer	Bladder cancer	Renal cancer
1.5	93.6%	84.0%	68.2%
2.0	>99.9%	99.6%	97.0%

For UK CPRD (GOLD and Aurum): observed IRs of 111.5, 66.7, and 26.5 per 100,000 person-years for UTC, bladder cancer, and renal cancer respectively, expected follow-up of 2.4, matching ratio of 1:3, and expected number of empagliflozin initiators of 16,360.

For Sweden: observed IRs of 164.5, 104.1, and 58.0 per 100,000 person-years for UTC, bladder cancer, and renal cancer respectively, expected follow-up of 2.2, matching ratio of 1:1, and expected number of empagliflozin initiators of 32,334.

For Finland: observed IRs of 161.5, 86.8, and 71.6 per 100,000 person-years for UTC, bladder cancer, and renal cancer respectively, expected follow-up of 2.4, matching ratio of 1:2, and expected number of empagliflozin initiators of 18,269.

The minimum detectable effect sizes for each outcome were computed given the observed and expected IRs, average follow-ups, matching ratios, and number of empagliflozin initiators for single-country analyses as well as for a random-effects meta-analysis (Table 9). At the meta-analysis level, the minimum detectable effect sizes were 1.37 for urinary tract cancers, 1.47 for bladder cancer, and 1.62 for renal cancer.

Table 9

Minimum detectable effect sizes (Hazard Ratios) given country-level observed incidence rate, expected sample sizes, expected average follow-ups, and matching ratios for single-country analyses and meta-analyses for a type 1 error probability of 5%.

	Urinary tract cancer	Bladder cancer	Renal cancer
UK CPRD¹	1.62	1.82	2.40
Sweden²	1.46	1.60	1.85
Finland³	1.50	1.70	1.78
Meta-analysis	1.37	1.47	1.62

1 Includes both CPRD GOLD and Aurum; Observed IRs of 111.5, 66.7, and 26.5 per 100,000 person-years for UTC, bladder cancer, and renal cancer respectively, expected follow-up of 2.4, expected number of empagliflozin initiators of 16,360, and matching ratio of 1:3.

2 Observed IRs of 164.5, 104.1, and 58.0 per 100,000 person-years for UTC, bladder cancer, and renal cancer respectively, expected follow-up of 2.2, expected number of empagliflozin initiators of 32,334, and matching ratio of 1:1.

3 Observed IRs of 161.5, 86.8, and 71.6 per 100,000 person-years for UTC, bladder cancer, and renal cancer respectively, expected follow-up of 2.4, expected number of empagliflozin initiators of 18,269, and matching ratio of 1:2.

UK CPRD=The United Kingdom Clinical Practice Research Datalink

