8.3.5 Follow-up time

For the primary AT analyses, the follow-up time (time at risk) will begin 6 months after the index date (lag period to account for empirical induction/promotion period of cancer) and end at urinary tract (bladder, renal or other) cancer or at any of the censoring events including discontinuation of index drug treatment.

For the sensitivity ITT analyses, the follow-up time will begin 6 months after the index date and end at urinary tract (bladder, renal or other) cancer or any of the censoring events excluding treatment discontinuation of index drug.

Patients with censored follow-up time will not be able to re-enter study cohort at a later time point. Follow-up will not be censored if oral or injectable glucose lowering drugs other than the index drugs are prescribed in addition to empagliflozin, a DPP-4 inhibitor, or a SGLT-2 inhibitor after the index date.

The lag period of 6 months is to account for an empirical induction/promotion period. Information in the first 6 months after the index date (i.e., first 6 months of follow-up) will be excluded, including patients with less than 6 months of follow-up and all occurrences of cancer within the first 6 months of follow-up, in order to consider a biologically meaningful induction/promotion time window. Sensitivity analyses will expand the lag period to 12 months.

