1 Includes both CPRD GOLD and Aurum; Observed IRs of 111.5, 66.7, and 26.5 per 100,000 person-years for UTC, bladder cancer, and renal cancer respectively and expected follow-up of 2.4.

2 Observed IRs of 164.5, 104.1, and 58.0 per 100,000 person-years for UTC, bladder cancer, and renal cancer respectively expected follow-up of 2.2.

3 Observed IRs of 161.5, 86.8, and 71.6 per 100,000 person-years for UTC, bladder cancer, and renal cancer respectively expected follow-up of 2.4.

HR=Hazard ratio; UK CPRD=The United Kingdom Clinical Practice Research Datalink

The average follow-up time required to achieve 80% power to detect HRs of 1.5 and 2.0 with the expected number of patients ([Table 6](#)) and observed IRs was evaluated for each of the study outcomes for the country-level analyses ([Table 12](#)) and for a random-effects meta-analysis ([Table 13](#)).

Table 12

Required follow-up time (years) to achieve 80% power in country-level analyses with a type 1 error probability of 5% for different effect sizes for the three primary endpoints given country-level observed incidence rates, expected sample sizes, and expected matching ratios

Matching	Hazard ratio	Urinary tract cancer	Bladder cancer	Renal cancer
UK CPRD¹				
1:3	1.5	3.03	4.73	11.13
	2.0	1.22	1.71	3.54
Sweden²				
1:1	1.5	1.99	2.86	4.73
	2.0	0.96	1.23	1.81
Finland³				
1:2	1.5	2.38	4.00	4.75
	2.0	1.05	1.53	1.75

1 Includes both CPRD GOLD and Aurum; Observed IRs of 111.5, 66.7, and 26.5 per 100,000 person-years for UTC, bladder cancer, and renal cancer respectively, expected number of empagliflozin initiators of 16,360, and matching ratio of 1:3.

2 Observed IRs of 164.5, 104.1, and 58.0 per 100,000 person-years for UTC, bladder cancer, and renal cancer respectively, expected number of empagliflozin initiators of 32,334, and matching ratio of 1:1.

3 Observed IRs of 161.5, 86.8, and 71.6 per 100,000 person-years for UTC, bladder cancer, and renal cancer respectively, expected number of empagliflozin initiators of 18,269, and matching ratio of 1:2.

UK CPRD=The United Kingdom Clinical Practice Research Datalink

Table 13

Required follow-up time (years) in each study country to achieve 80% power for the meta-analysis with a type 1 error probability of 5% for different effect sizes for the three primary endpoints given country-level observed incidence rates, expected sample sizes, and expected matching ratio

Matching	Hazard ratio	Urinary tract cancer	Bladder cancer	Renal cancer
UK CPRD¹				

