8.7.1.4 Comparative analyses

Relative risks (HRs) for the defined outcomes will be estimated using Cox models with time-varying covariates if model pre-requisites are fulfilled. HRs will be presented along with 95% CIs.

The Cox models will include the exposure and the comparator group within the model. This will account for multiple testing and for retaining same variables in variable selection (see [Section 8.7.1.6](#)). The models are defined in terms of covariates adjusted for in addition to the primary exposure: (i) baseline model with covariates adjusted for with values at index date (ii) model with time-dependent covariates wherein change in covariates over the follow-up period after index date are also incorporated into the model.

Country-specific analysis:

The country-specific Cox models will be fit with single-country level datasets. The analyses will use datasets from the UK, Sweden, and Finland, separately.

Meta-analysis:

Country-level effect sizes will be pooled using meta-analysis models to compute pooled effect size estimates. Prior to conducting meta-analyses, heterogeneity across the countries in terms of study design and conduct will be assessed. Specifically, the variability in population characteristics (including data availability), propensity score matching variables as well as propensity score balance will be examined.

Meta-analyses will be carried out for analyses where the country-level effect size is available for all three study countries. Pooled effect sizes will be estimated using random-effects models. The inverse-variance method will be used where appropriate.

Statistical heterogeneity between country-level estimates will be assessed using:

- Cochran's Q test
- I^2 statistic and its 95% CI
- The τ^2 statistic and its 95% CI

For each meta-analysis model, results will be presented in a forest plot including at least the following data:

- Data source.
- Effect size and 95% CI for each study included in the analysis (on a log scale).
- The weights allocated to each study.
- The combined estimated effect size with 95% CI (on a log scale) for the random-effects model.
- Value of Cochran's Q statistic, with the number of degrees of freedom and p-value.
- The proportion of variability explained by heterogeneity (I^2).
- The between-study variance τ^2 .

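### The UK power and sample-size figures in Protocol 8.5 fit about 2.2 years of follow-up and 16,887 initiators, not the stated 2.4 years and 16,360, and one Table 10 cell (25,810) does not fit its own column

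*Protocol*

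**What the plan says.** Protocol 8.5 gives the planning inputs by country: "The expected averages of follow-up time were 2.4 years for UK CPRD, 2.2 for Sweden, and 2.4 for Finland", attributed to the fifth interim report. The UK footnotes to Tables 7 and 8 read "expected follow-up of 2.4, matching ratio of 1:3, and expected number of empagliflozin initiators of 16,360". Table 9 gives the same three inputs, and the footnotes to Tables 10 and 11 repeat the 2.4 years. The footnotes to Tables 12 and 13 again give 16,360 initiators. The abstract gives 16,887 for the UK, and Table 6 agrees (8,342 GOLD + 8,545 Aurum = 16,887).

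The UK rates are "Observed IRs of 111.5, 66.7, and 26.5 per 100,000 person-years for UTC, bladder cancer, and renal cancer respectively". Matching is 1:3 in the UK, 1:1 in Sweden and 1:2 in Finland.

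Section 8.3.5 says that in the primary analysis "the follow-up time (time at risk) will begin 6 months after the index date". Section 8.5 does not say whether that half-year was taken off the expected follow-up. It gives no formula for the single-country figures beyond saying that they rest on Cox-model hazard ratios.

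**The concern.** The UK and Finland are stated to share 2.4 years, and Sweden has 2.2. Table 13, captioned "Required follow-up time (years) in each study country to achieve 80% power for the meta-analysis", shows a different grouping. At HR 1.5 the UK row is 1.38, 2.05, 3.08 and the Swedish row is 1.38, 2.04, 3.07, while Finland has 1.50, 2.22, 3.35. The UK behaves like the 2.2-year country.

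If so, either the stated UK follow-up or the UK results computed from it are wrong. The UK power was updated at EMA's request to take the added CPRD Aurum data into account, and a reader cannot reproduce it from what is printed. The two values for UK initiators add to the difficulty.

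**Working it through.** **Inputs.** Rates, follow-up, matching ratios and numbers are those of Protocol 8.5. Target: "with at least 80% power and a type 1 error probability of 5% under the expected matching ratios". Sidedness is not stated. I take it as two-sided, because 8.7.1.4 says "HRs will be presented along with 95% CIs". The observed rate is used for the DPP-4 arm and HR × rate for empagliflozin. 8.5 says this for the simulation, and I assume it for the single-country figures.

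**Formulas.** T is time at risk, r comparators per initiator, k = 1/r, pC = 1 − exp(−IR·T), pE = 1 − exp(−IR·HR·T).

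- Wald: N = (1.960 + 0.842)² × (1/pE + 1/(r·pC)) / (ln HR)²
- Freedman: m = (1/k) × ((k·HR + 1)/(HR − 1))² × (1.960 + 0.842)²; N = m·k/(k·pE + pC)

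**Reproducing the plan's own figures.** Sweden, all urinary tract cancers, HR 1.5, T = 2.2 − 0.5 = 1.7: pC = 0.002793, pE = 0.004186, so N = 7.849 × (238.9 + 358.1)/0.1644 ≈ 28,500 (printed 28,151). Without the deduction Sweden gives 21,739–22,035, more than 20% too low.

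Table 10, required N at HR 1.5 (all urinary tract / bladder / renal):

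| Country, T | Printed | Wald | Freedman |
|---|---|---|---|
| Sweden, 1.7 (stated) | 28,151 / 44,523 / 79,991 | 28,501 / 45,010 / 80,748 | 28,118 / 44,403 / 79,654 |
| Finland, 1.9 (stated) | 17,999 / 33,543 / 40,665 | 18,188 / 33,809 / 40,979 | 17,939 / 33,348 / 40,420 |
| UK, 1.9 (stated) | 25,810 / 41,550 / 104,474 | 22,568 / 37,704 / 94,852 | 22,257 / 37,188 / 93,559 |
| UK, 1.7 | same | 25,219 / 42,136 / 106,007 | 24,872 / 41,560 / 104,563 |

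At HR 2.0 the UK at T = 1.9 gives 6,437 / 10,753 / 27,049 (Wald) or 6,184 / 10,331 / 25,990 (Freedman), against printed 7,072 / 11,846 / 29,788. All six UK values at the stated input are 9–14% below print. Wald matches all twelve Swedish and Finnish cells within 1.3%. Freedman is about 3% low at HR 2.0.

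Table 7, UK power at HR 1.5 (printed 63.7 / 43.1 / 20.3%):

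| T, N | Wald | Freedman |
|---|---|---|
| 1.9, 16,360 (stated) | 66.5 / 45.4 / 21.3 | 67.1 / 45.9 / 21.5 |
| 1.7, 16,360 | 61.7 / 41.5 / 19.5 | 62.3 / 42.0 / 19.7 |
| 1.7, 16,887 | 63.0 / 42.6 / 20.0 | 63.6 / 43.1 / 20.2 |

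Table 9 behaves the same way. Printed UK detectable HRs are 1.62 / 1.82 / 2.40. T = 1.7 with 16,887 gives 1.61–1.62 / 1.81–1.82 / 2.36–2.41, and the stated inputs give 1.59 / 1.78–1.79 / 2.30–2.34.

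**Checks that need no power formula.**

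1. *Table 12 against Table 10.* With events this rare, N × T is nearly constant, so (Table 12 years − 0.5) × expected N / Table 10 N returns the time at risk behind Table 10. Sweden's six cells give 1.710–1.722 and Finland's 1.904–1.915. Five UK cells give 1.718–1.725 with N = 16,887; for bladder at HR 1.5, 4.23 × 16,887/41,550 = 1.719. With 16,360 those five give 1.665–1.671, also far from 1.9. The sixth, 25,810, gives 1.655 with 16,887 and is the only outlier of 18. A straight line of Table 12 on Table 10 has intercepts 0.505, 0.502 and 0.505 (Sweden, Finland, UK without 25,810), so the half-year is visible in the tables themselves.
2. *Table 13.* The six Finland/UK ratios are 1.083–1.095, and 2.4/2.2 = 1.091. The UK and Swedish cells agree within 0.01 despite different rates and numbers, which suggests that each row is a common multiple of that country's expected follow-up.
3. *Number of initiators.* Table 12 does not use expected follow-up. Wald plus 0.5 year gives 3.04 / 4.75 / 11.19 with 16,887 and 3.12 / 4.88 / 11.53 with 16,360; printed 3.03 / 4.73 / 11.13. In Table 11, Sweden/UK is 29,687/15,505 = 1.915. 32,334/16,887 is also 1.915, while 32,334/16,360 = 1.976.
4. *25,810.* At fixed HR and ratio, N scales inversely with incidence: 41,550 × 66.7/111.5 = 24,855 and 104,474 × 26.5/111.5 = 24,830. The printed value is 3.8–3.9% higher.

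**Effect on the meta-analysis.** I used inverse-variance weights 1/(1/dE + 1/dC + 0.1²) per country, where dE and dC are expected events. Moving the UK from T = 1.7 to 1.9 at N = 16,887 changes power at HR 1.5 from 97.3 to 97.5%, 89.2 to 89.9% and 73.4 to 74.2%. This approximation lies above the printed Table 8 levels, so I use it only for the change, at most 0.8 point.

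**The case against.** The sponsor's single-country formula, sidedness and lag deduction are all inferred, and the fifth interim report is not available here. So the figures can only be called consistent with 2.2 years. That stands. It does not rescue 2.4: Schoenfeld, Freedman and Wald variants were tried with and without the lag, and none fits the UK tables at 2.4 years. Schoenfeld with the rate taken as overall comes near the HR 1.5 powers (64.1 / 43.5 / 20.4%) but gives 86.7% and 49.0% at HR 2.0 for bladder and renal, against printed 91.7% and 55.9%. The Table 13 pattern needs no power formula.

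The replacement for 25,810 does depend on the formula: at T = 1.7 Wald gives 25,219, only 2.3% below print, and Freedman 24,872. The column scaling and the Table 12 comparison are the firmer evidence. A one-digit slip from about 24,810 would fit but cannot be shown.

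Some cells hardly move. At the stated inputs, power for all urinary tract cancers at HR 2.0 is 99.4–99.5% against 99.1%.

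A reader might infer that the study is underpowered, or that the UK figures were shaped to support adding Aurum. Neither is supported. 8.5 claims adequacy at the meta-analysis level, and the protocol records that EMA asked both for Aurum to be reconsidered and for the update.

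**Conclusion.** The UK figures in Tables 7, 9, 10 and 13 do not follow from their stated inputs. They fit about 2.2 years (1.7 at risk) and 16,887 initiators. At the stated 2.4 years and 16,360, UK power at HR 1.5 is about 3 points higher for all urinary tract and bladder cancer and about 1 point higher for renal cancer. This rests on a two-sided 5% test, constant hazards, the observed rate in the DPP-4 arm and the half-year deduction, which Sweden and Finland confirm.

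It would be tempting to conclude that 2.4 is simply a misprint for 2.2. The documents do not settle that. If 2.4 is right, the printed UK power is conservative. If 2.2 and 16,360 were both right, it would be about 1 to 2 points too high for all urinary tract and bladder cancer, and less for renal. Meta-analysis power changes by under about one point, so the adequacy conclusion does not change. This is a correction worth making, not a design flaw.

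**What to change.** Check the UK follow-up in the fifth interim report.

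- If 2.2 years is right, change the UK value in the 8.5 text and in the footnotes of Tables 7–11.
- If 2.4 is right, reissue the UK columns of Tables 7, 9, 10 and 13, and rerun or confirm the meta-analysis figures in Tables 8, 9, 11 and 13.

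In either case:

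- Reconcile the UK number of initiators: 16,360 in the footnotes of Tables 7, 8, 9, 12 and 13 against 16,887 in the abstract and Table 6.
- Recompute and replace 25,810 with the sponsor's own formula, and name that formula.
- State that 0.5 year is deducted from expected follow-up, and that the required follow-up in Tables 12 and 13 includes it.

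The cost is a text and table correction, with a rerun of existing simulation code at most. No new data are needed.

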Matching will be performed for empagliflozin initiators with patients initiating DPP-4 inhibitors within each country database. Matching will be carried out in several rounds to achieve the highest possible matching ratio given the available data in each country (up to 1:3 matching) [[P12-07757](#)]. In the first round of matching, for each empagliflozin initiating individual i with a particular index date T_{iE} , all individuals initiating other DPP-4 inhibitors within three months before or after T_{iE} will be chosen. Of these, one individual with the closest PS to that of i within a predefined PS interval will be selected as a match (Greedy matching method). The predefined PS interval will be calculated based on the standard deviation of the logit of PS (δ) multiplied by some coefficient k (say, $k\delta$, when $k=0.2$). The value of the coefficient k will be calibrated to ensure at least 99% of those exposed to empagliflozin have matches from each comparator. The selected comparators are then removed from the pool of the possible comparators for further selection (sampling without replacement). Once the first round of matching is done, additional rounds of matching will be carried out to identify a second and possibly a third match for each already matched for each empagliflozin initiating individual (variable ratio matching with 1:3 as the maximum ratio). The number of matched DPP-4 inhibitors, and hence the overall matching ratio, will therefore be maximized within each country. Matching by time period, based on index dates, enables better control of time-varying confounders including changing prescription patterns for empagliflozin and potential confounding.

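### The matching ratios assumed for Finland (1:2) and the UK (1:3) cannot be supplied within the three-month matching window, so Finland's single-country power and required N are too favourable

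*Protocol*

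**What the plan says.** Protocol 8.5 (Study size) expects that "the maximum achievable matching ratios will be 1:3 for UK CPRD (GOLD and Aurum), 1:1 for Sweden, and 1:2 for Finland". It fixes these ratios in every power calculation and adds: "These are the highest achievable matching ratios given expected patient numbers". Table 7 then gives Finland 80.6% power for urinary tract cancer (UTC) at HR 1.5, and Table 10 gives a required 17,999 Finnish empagliflozin initiators against 18,269 expected.

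The matching rule is in Protocol 8.7.1.1. For each empagliflozin initiator the eligible pool is "all individuals initiating other DPP-4 inhibitors within three months before or after" that patient's index date. Each comparator is used once, and up to three rounds are run.

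SAP 6.5.2 repeats the window as 90 days, requires the same metformin status, and in the UK confines matching to the same CPRD database. SAP 6.3 goes further and names index year as an exact matching criterion. SAP 6.5.2 also says that loosening the time restriction will be considered if matches per patient prove strongly uneven over time.

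**The concern.** Whether a ratio is achievable under a three-month window depends on the supply of comparators in each period, not over the whole study. Table 6 shows the two drugs moving in opposite directions. DPP-4 initiators per empagliflozin initiator in Finland are 5.18 in 2016, 1.99 in 2017, 1.62 in 2018, 1.19 in 2019 and 0.80 in the first half of 2020. In GOLD they fall from 3.29 in 2017 to 2.71, 1.96, 1.43 and 1.08 in 2021. Most empagliflozin initiators come late, when comparators are scarce.

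If the ratios cannot be met, the Finnish and UK entries in Tables 7, 9, 10 and 12 describe a design that the matching rule does not produce. Finland matters most, because Tables 7 and 10 show it just passing 80% for UTC at HR 1.5.

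**Working it through.** **1. Can Table 6 supply the ratios?** This step needs no assumption about timing within a year. Every DPP-4 initiator in the preceding calendar year is counted as eligible, although the window reaches back only three months.

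- Finland, 2018 to June 2020: 4,293 + 5,182 + 2,777 = 12,252 empagliflozin initiators, so 1:2 needs 2 × 12,252 = 24,504 comparators. All DPP-4 initiators from January 2017 on: 7,402 + 6,959 + 6,158 + 2,215 = 22,734.
- GOLD, 2019 to 2021: 1,846 + 1,541 + 969 = 4,356 initiators, so 1:3 needs 13,068. All DPP-4 initiators from January 2018 on: 4,158 + 3,622 + 2,210 + 1,051 = 11,041.

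Because UK matching stays within one database and is capped at three, surplus Aurum comparators cannot lift the UK mean back to 3.

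**2. What mean ratio is attainable?** These are upper bounds, before the propensity-score caliper and exact metformin matching.

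- Same index year (SAP 6.3), Finland, the sum over years of min(cap × E, D): cap 2 gives 27,318/18,269 = 1.50; cap 3 gives 29,610/18,269 = 1.62.
- Window of one adjacent quarter either side, counts spread evenly within each year, solved as a linear program: Finland 1.60 (cap 2) or 1.77 (cap 3).
- GOLD, cap 3: 18,391/8,342 = 2.20 (same year) or 2.34 (window). With Aurum assumed at the full 1:3, the UK mean is (18,391 + 3 × 8,545)/16,887 = 2.61, or 2.67 with the window.

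**3. Reproducing the Finnish figure.** The footnote inputs are "Observed IRs of 161.5, 86.8, and 71.6 per 100,000 person-years for UTC, bladder cancer, and renal cancer respectively, expected follow-up of 2.4", with "matching ratio of 1:2, and expected number of empagliflozin initiators of 18,269". The simulation text takes "the observed incidence rates as the baseline rate in the DPP-4 cohort", so the empagliflozin rate is HR times that. Two-sided 5% is assumed. The formula is of Freedman type:

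power = Φ( √(k·m) × (HR − 1)/(k·HR + 1) − 1.96 ), with k = nE/nC, m = expected events and p = 1 − exp(−rate × t).

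With t = 2.4 − 0.5 = 1.9 years (the six-month lag removed), pC = 0.00306 and pE = 0.00459. At 1:2, m = 18,269 × 0.00459 + 36,538 × 0.00306 ≈ 195.8 and k = 0.5. Then √97.9 × 0.5/1.75 − 1.96 = 0.867, so power is 80.7% (stated 80.6%). Required N is 17,939 (stated 17,999). Bladder and renal cancer give 54.5% and 47.0% (stated 54.3% and 46.7%). Sweden with t = 1.7 gives 85.2% (stated 85.1%).

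**4. Finland, UTC, HR 1.5, at attainable ratios**

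| Mean ratio | Basis | Power | Required N |
|---|---|---|---|
| 2.00 | as assumed | 80.7% | 17,939 |
| 1.77 | window, cap 3 | 78.6% | 18,918 |
| 1.62 | same year, cap 3 | 76.9% | 19,737 |
| 1.60 | window, cap 2 | 76.6% | 19,879 |
| 1.50 | same year, cap 2 | 75.3% | 20,537 |

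Every required N below the first row exceeds the 18,269 expected.

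**5. UK.** Stated power of 63.7% is reproduced (63.6%) only with N = 16,887 and t = 1.7 years; the footnotes give 16,360 and 2.4. On the reproducing inputs, ratios of 2.61 to 2.67 give 61.5% to 61.9%.

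**6. Meta-analysis.** A random-effects simulation with the stated standard deviation of 0.1 and a threshold of 0.05 (8.5 prints 0.5) gives 93.0% for UTC at HR 1.5, 82.5% for bladder cancer at HR 1.5 and 97.2% for renal cancer at HR 2.0, against the stated 93.6%, 84.0% and 97.0%. With attainable UK and Finnish ratios and Sweden at about 1:1, the results are about 92%, 81-82% and 97%.

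**The case against.** Five points can be made for the plan.

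- **The adequacy claim is made at the meta-analysis level.** This stands. A reader might infer that the study is underpowered; the documents do not support that, because pooled power stays above 80% for the targeted effects, though bladder cancer is close.
- **The sub-80% Finnish result rests on an inferred time at risk.** This stands in part. The protocol nowhere says that six months were deducted. With 2.4 years a Schoenfeld calculation gives 82.5-84.2% at ratios of 1.5 to 1.77. But it gives 85.3% at 1:2, so it does not reproduce the stated 80.6%. It would be too strong to say that Finland definitely falls short.
- **Matching is variable up to 1:3.** The shortfall in step 1 rules out two comparators for every Finnish initiator. It does not by itself rule out a mean of 2: with adjacent years fully open and a cap of 3, the mean could reach 2.23. That requires comparators up to a year or more outside the window. With even spread within each year the figure is 1.77, and under the SAP's exact index year it is 1.62 with no timing assumption.
- **The SAP foresees uneven matches over time.** It commits only to considering a relaxation, and relaxing would weaken the calendar-time control that both documents give as the reason for the window. The caution in 8.5 that fewer patients may be available for analysis does not qualify the ratios.
- **The ratios were set cautiously.** A reader might infer that they were simply read off the all-years totals. They were not: Sweden's total is 68,481/32,334 = 2.12 but 1:1 is used, and Finland's is 54,079/18,269 = 2.96 but 1:2 is used. Nor is Sweden's 1:1 an error. A higher Swedish mean (up to about 1.7) is only an upper bound under perfect overlap, so 1:1 is a defensible conservative value.

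**Conclusion.** The point holds for Finland and the UK. Table 6 and the matching rule contradict the statement that 1:2 and 1:3 are achievable.

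For Finland, UTC power at HR 1.5 is overstated by about 2 to 5 points and required N is understated by roughly 900 to 2,500. This rests on even initiation within each year (or on the SAP's exact index year) and on the 1.9 years that reproduce Table 7. The attainable ratios are ceilings, so further losses to the caliper and metformin matching are possible.

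For the UK the loss is about 2 points, assuming Aurum reaches 1:3; Table 6 gives no yearly Aurum counts to test that. UK power at HR 1.5 was already below 80%.

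The pooled conclusion is unaffected. This is a correction to stated figures, not a reason to change the design.

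**What to change.** Re-run the Finland and UK entries of Tables 7, 9, 10 and 12, and the meta-analysis figures in Tables 8, 9, 11 and 13. Use the mean ratio attainable within the 90-day window by calendar period, and within database for the UK. In Protocol 8.5 and the matching sentence of the abstract, replace the claim about achievable ratios with those means and say how they were obtained. State the time at risk used for each country, and reconcile the UK N (16,360 or 16,887). Add that Finland alone is not shown to reach 80% for UTC at HR 1.5 under the method that reproduces Table 7. Sweden may stay at 1:1, labelled as conservative.

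The cost is one re-run of existing power code plus yearly Aurum counts if they can be obtained. A few single-country figures become less favourable; no change to data, matching or analysis is needed.
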